Assess. Each morning, participants will be prompted to complete a daily diary to assess the following from the previous day: number of cigarettes smoked, NRT use, and tobacco craving. Because ongoing smoking during cue-exposure sessions will be counter-productive to extinction of urges, participants will need to self-report 48 hours of abstinence to advance to Setup. Achieving such short-term abstinence with quitline support/NRT should be feasible for at least 70% of participants (Shiffman et al., 1996; Shiffman et al., 2007).

Setup. Once the abstinence requirement is met, participants will personalize the app, learn the purpose of the app, and practice using AR. First, they will watch a video tutorial explaining the use of cue exposure. They will select their most relevant AR cues and situations in which they most commonly smoke and/or experience high cravings (e.g., upon waking, after meals, when stressed, with alcohol, with coffee, celebrating). They will receive a list of “best practices” for completing AR sessions (e.g., no smoking during sessions). Participants will next receive instruction on using the app for cue-exposure sessions, comprising a short video describing how to place the AR objects, followed by an interactive tutorial with real-time practice.

Recommendations for Use. Recommendations for daily use will be proactively provided, but also available for later review on demand. The app will recommend that participants complete 2-5 AR sessions per day. It will emphasize that the more often they use the app when experiencing craving, the more successful they will likely be in maintaining abstinence.

Extras. Participants will be introduced to all other features of the app: setting up reminder notifications, accessing the progress tracker, access to the App coach, and viewing of rewards.

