The Florida Tobacco Quitline is operated by RVO Health, the largest provider of tobacco cessation quitlines in the U.S. RVO Health's Quit For Life® program is an evidence-based tobacco cessation treatment delivered over phone, web, and text, and is grounded in social cognitive theory and the U.S. Public Health Service clinical guidelines (PHS Guideline, 2008). Quitline coaches use cognitive behavioral therapy, reinforcement, and principles of self-efficacy to promote effective behavior change. The quitline approach includes 5 key elements: setting a quit date, coping with triggers, effectively using medications, tobacco proofing, and social support. Phone counseling for cessation has been evaluated in randomized trials and effectiveness studies (Hollis et al., 2007; Orleans et al., 1991; Stead et al., 2013; Zhu et al., 2002). Individuals who enroll in the quitline's multi-call program receive three phone calls. They are mailed two weeks of NRT after the first phone call, to begin using on their quit date (coinciding with the second call). Participants will be provided with information about the study during their first phone call, and study staff will reach out to enroll participants in the study after receiving their contact information from the Quitline.

Study Arms

Quitline Only (QLO). Participants randomized to the QLO condition will receive an app that administers the daily diary questions for 5 weeks and shows their app and abstinence related progress. They will not receive any treatment via the app. Thus, they will receive usual care via the quitline and complete minimal daily assessments.

Quitline plus AR (QL+AR). Participants randomized to QL+AR will receive the AR app described in Aim 1. Initially, the app will only administer the daily diary questions. Once 48 hours of self-reported tobacco abstinence is achieved, the AR elements of the app will become available (see 4.2). Daily diary questions will continue for 5 weeks. AR extinction trials will occur daily until (1) the participant reports 3 consecutive days of smoking, in which case the AR trials will be suspended until another smoke-free 48 hours are reported, or (2) a

total of 5 weeks have elapsed since the start of app use.

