indicator of treatment engagement. Primary treatment engagement variables of interest that are linked to our theoretical model of extinction and that are related to increased abstinence include: greater completion of the AR sessions (e.g., multiple times per day over several days), conducting the AR sessions in several different locations (to increase generalizability of extinction), and less use of avoidance strategies during the AR sessions (e.g., using distraction or other behaviors to avoid experiencing craving). Avoidance strategies will be assessed at the 5 week survey via a checklist of avoidance strategies and the frequency that they occurred during AR sessions. We will also collect self-reported treatment satisfaction using a modified version of the Client Satisfaction Questionnaire (Attkisson & Greenfield, 1994), the SUS (Brooke et al., 1996; Lewis & Sauro, 2009), and unique items to assess features and functions of the app and the AR experience, including the App coach. Extinction magnitude (degree of craving reduction over time) and latency (time to meeting extinction criteria) will also be derived. For participants who never achieved abstinence during the 5 weeks of app use, thus, never completed AR sessions, versions of the follow-up surveys will omit items specifically related to AR use. For participants who achieved abstinence, but did not complete more than 4 AR sessions, there will be questions at the 5-week survey regarding barriers to completing the AR sessions.

Quitline Usage and App Coaching. Basic information on participant interactions will be provided to the study team from the quitline, including call completion dates, quit status (planned and actual quit dates), and NRT that was shipped. For those in QL+AR, we will track calls completed with an App coach.

Tobacco Abstinence. The primary outcome measure will be 7-day point prevalence abstinence (defined as self-report of no combustible tobacco use in the past 7 days; Piper et al., 2020) around 6 months post-baseline. Reported abstinence will be confirmed in approximately 40% of self-reported abstinent participants using a saliva cotinine level cut-off of <10 ng/ml (Benowitz et al., 2020). Cotinine analysis using ELISA assay will be conducted by Salimetrics (Carlsbad, CA).

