Aim 2a. The primary test of the efficacy of QL+AR over QLO will use logistic regression on biochemically-confirmed abstinence around 6 months after baseline survey completion. This will be performed on the 20 imputed data sets using those participants who exhibited 48 hours of abstinence (n=1450). The model will include demographics and smoking-related variables that were found to uniquely predict self-reported abstinence at 6 months based on preliminary analyses. A parallel analysis will be performed to evaluate efficacy for all enrolled (N=2072; i.e., beyond those who exhibit the required 48-hour abstinence to engage the AR intervention). A second test of effectiveness will use generalized estimating equations (GEE) with both the 5-week and 6-month abstinence as the outcomes. This approach permits evaluation of a change in abstinence from around 5 weeks to 6 months and an assessment of the intervention at around 5 weeks in the context of the primary outcome (using a timespecific contrast).

Aim 2b. Prospective moderators of the QL+AR intervention will be explored, separately, by extending the analyses described above through the inclusion of the moderator and the moderator x intervention as predictors of the dependent measure. A significant interaction term supports the variable as a moderator, which will be explored by assessing condition differences for each level of categorical moderators and for levels of continuous moderators created via median splits, tertiles, or quartiles. The following baseline measures will be evaluated: sex, nicotine dependence, trait cue reactivity, smoking status during treatment, quitline use, and NRT use.

Prospective predictors of the AR intervention will be evaluated using only participants from the QL+AR arm. Similar to the analyses described above, AR-related variables will be added to a logistic regression model of abstinence at around 6 months that includes demographics and baseline smoking-related variables found to be predictors of abstinence among QL+AR participants. The following variables will be explored: initial cue reactivity, extinction magnitude and latency, indices of treatment engagement, and App coach use.

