Aim 3a. Our preliminary cost-effectiveness assessment will use the primary trial endpoint of smoking abstinence at around 6 months as the main effectiveness/outcome measure. Using this outcome, we will calculate the incremental cost-effectiveness of the QL+AR arm compared to the QLO arm in increasing smoking abstinence

(e.g., cost per quitter). Finally, we will also use quality adjusted life years (QALYs) and lifetime medical costs to estimate more inclusive, life-long effect and cost-effectiveness of the intervention. We will use the most recent estimates in the literature (e.g., Feirman et al., 2016; Kaplan et al., 2007) to estimate QALYs and lifetime medical costs associated with smokers and smoking cessation. We will assess the robustness of incremental results between the two study arms using probabilistic sensitivity analysis. Cost-assessments and cost effectiveness will be calculated on the basis of both all enrolled participants as well as only those who qualified for the AR intervention by achieving 48 hours of abstinence.

Aims 3b and 3c. Descriptive statistics will be used to evaluate treatment engagement (measured via greater completion of the AR sessions, conducting the AR sessions in several different locations, and less use of avoidance strategies during the AR sessions), acceptability (measured via the Client Satisfaction Questionnaire, System Usability Scale, and unique items that assess app features, functions, and the AR experience including the App coach). Variables derived from engagement with the app will be explored as predictors in multivariable models that already include baseline predictors.

Qualitative methods will be used to identify facilitators and barriers to app usage. We will use thematic analysis to analyze the key stakeholder interviews (quitline supervisors, App coaches, subset of participants; Creswell, 2007). We will develop a list of a priori codes based on the domains identified in the interview guide to develop an initial codebook. Two trained qualitative analysts from Moffitt's Participant Research Interventions and Measurement Core will independently code an initial set of transcripts (n=5). After the first round of coding is complete, they will discuss their notes on possible new codes (e.g., themes that emerge from the data) and refine the codebook. The analysts will code another initial set of transcripts (n=5) and

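### Cumulative AR session and extinction measures are tested as predictors of 6-month abstinence although AR access depends on early abstinence, so an association is expected even if AR has no effect

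*Combined protocol and SAP*

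**What the plan says.** **Access to AR.** Section 4.2 (Assess) states that "participants will need to self-report 48 hours of abstinence to advance to Setup". Section 4.3 (Study Arms) repeats the rule: "Once 48 hours of self-reported tobacco abstinence is achieved, the AR elements of the app will become available". After 3 consecutive days of reported smoking, "the AR trials will be suspended until another smoke-free 48 hours are reported". Section 4.4 acknowledges that participants who never became abstinent during the 5 weeks complete no AR sessions.

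**The predictors.** Section 4.4 defines engagement first as "greater completion of the AR sessions (e.g., multiple times per day over several days"), then as use in several locations and less avoidance during sessions. Extinction magnitude and latency are derived from urge ratings in the same sessions.

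**The models.** In Section 5, Aim 2b, the predictors "will be evaluated using only participants from the QL+AR arm". They are added to a logistic model of 6-month abstinence "that includes demographics and baseline smoking-related variables found to be predictors of abstinence among QL+AR participants". The list is "initial cue reactivity, extinction magnitude and latency, indices of treatment engagement, and App coach use". Under Aims 3b and 3c, "Variables derived from engagement with the app will be explored as predictors in multivariable models" that already contain baseline predictors.

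**Analysis sets.** The Data Analysis Overview in Section 5 runs every analysis twice, in those who reached 48 hours of abstinence and in the full sample. The same section expects 5-week smoking status to be a primary predictor of 6-month status. It puts that variable in the imputation model; the predictor models do not name it.

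**The concern.** Someone who stays smoke-free unlocks early, is never suspended, and has most of the 5 weeks in which to accumulate sessions, visit locations and reach an extinction criterion. Someone who keeps relapsing has fewer available days, and someone who never reaches 48 hours has none. Early abstinence therefore drives the predictor through the access rule and drives the outcome through persistence of abstinence. Baseline covariates do not block that path.

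What is at stake is the reading of the engagement results. Section 4.4 ties these measures to the study's extinction theory and to increased abstinence. Section 4.2 has the app tell users that more frequent use should bring more success, and Section 6 plans a paper on theory-based mediating variables. In that setting, an association created by the access rule would easily be taken for a dose-response of AR.

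**Working it through.** **1. The plan's own power figures (Section 5).** Inputs: 725 per arm, 10% v 15%; and 1036 per arm, 7% v 10.6%; two-sided alpha .05. The 5% variance allowance is treated as n x 0.95. For two proportions with pooled rate p, power = Phi[(d - 1.96 x SE0) / SE1], with SE0 = sqrt(2p(1-p)/n) and SE1 = sqrt((p1(1-p1) + p2(1-p2))/n).

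- 48-hour set: n = 725 x 0.95 = 688.75, p = 0.125, SE0 = 0.01782, SE1 = 0.01777. (0.05 - 0.03493)/0.01777 = 0.848, so power is 0.802.
- Full set: n = 1036 x 0.95 = 984.2, p = 0.088, SE0 = 0.01277, SE1 = 0.01275. (0.036 - 0.02503)/0.01275 = 0.860, so power is 0.805.

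Both agree with the stated .80, and the odds ratios (1.588 and 1.575) agree with the stated 1.59 and 1.57. These rates can be used as the plan's expectations.

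**2. What those rates imply for participants who never unlock.** Per arm, 1036 - 725 = 311.

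- QLO: 7% x 1036 = 72.5 abstinent in all; 10% x 725 = 72.5 among those reaching 48 hours. Remainder: about 0 of 311.
- QL+AR: 10.6% x 1036 = 109.8; 15% x 725 = 108.75. Remainder: about 1 of 311 (0.3%).

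In the full QL+AR arm, zero sessions therefore almost determines non-abstinence. The same holds in QLO, where there is no AR, so the pattern is not evidence about AR.

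**3. Null simulation under the access rules.** From the documents: 1036 participants, 35 diary days, AR on after 2 smoke-free days and off after 3 consecutive smoking days, about 70% ever unlocked, 10% abstinent at 6 months among the unlocked. AR has no effect; 6-month abstinence depends only on smoking in week 5.

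Assumed, because the documents give no figures: spread of quitting propensity (SD 1-3 logits), day-to-day persistence of smoking (1-2 logits), 0.5-2 sessions per unlocked day with log-SD 0.5-1.0 and unrelated to quitting propensity, about 20 sessions (SD 6) to reach extinction, and a 1% daily chance of on-demand coach contact while unlocked. Models were univariable, with 200-300 simulated trials per scenario.

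Share of trials significant at a nominal 5%:

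| Predictor | Full QL+AR arm | 48-hour set |
|---|---|---|
| Session count | 80-100% | 25-96% |
| Extinction magnitude | 98-100% | 51-65% |
| Extinction latency, calendar days | 70-100% | 31-97% |
| On-demand coach contact | about 70% | 29-32% |
| Triggered coach contact | 4-39% | 3-4% |

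The odds ratio per SD of session count was 1.25-1.69 in the full arm and 1.14-1.45 in the 48-hour set. In the 48-hour set, 6-month abstinence was 3-6% in the lowest quarter of sessions and 13-17% in the highest. Locations used were not simulated; the argument carries over because distinct locations accrue with sessions.

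**4. Is the access rule the cause?** With the rule switched off, the rate for session count fell to 3-4.5%. With the rule kept and week-5 smoking added to the model in the 48-hour set, it was 2-5.5%.

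**5. Does a per-opportunity measure help?** In a further null simulation with the same 10% rate among the unlocked, session count was significant in 99-100% of trials (full arm) and 41-95% (48-hour set). Sessions per unlocked day gave 1-6% when rate of use was unrelated to quitting propensity, but 27% when the two were correlated at 0.3.

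**The case against.** The plan already includes the 48-hour set, and it calls these analyses exploratory without claiming a causal effect. Both are true. Restriction, however, removes only the first lock: time to unlock and later suspension still differ between participants, and the 48-hour column above shows what remains.

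Session count is not simply a count of smoke-free days. Suspension needs 3 consecutive smoking days, so intermittent smokers stay unlocked, and the app metadata would allow ratio measures. This stands, and it is one reason the association in the 48-hour set is only more likely and not certain.

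A reader might infer that the whole predictor list is contaminated. The documents do not support that. Initial cue reactivity does not accumulate with abstinent time. Avoidance comes from a 5-week checklist. Triggered coach contact starts from non-use of AR (Section 4.3), showed no inflation in the 48-hour set, and could even run the other way. A reader might also infer that this regression decides whether App coaches are kept; Section 4.3 links that to monitoring of the frequency, content and time of coaching.

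Adjusting for smoking during weeks 1-5 is open to a fair criticism: such smoking follows AR exposure and is a plausible route by which AR would work, so adjustment can remove a real effect. It was tested here only with no effect present. Finally, the per-day measure performs well only if rate of use is unrelated to motivation, which the documents cannot establish.

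**Conclusion.** The concern holds for cumulative session completion, number of locations, and extinction magnitude and latency as Aims 2b and 3b would analyse them. In the full QL+AR arm an association without any AR effect is near certain, and the plan's own rates show why without simulation. In the 48-hour set the chance is raised, at about 25-96% for session count; its size depends on assumed variability in use and smoking, but the positive direction held in every gated scenario. The simulations contained no baseline covariates, so the planned adjustment could reduce these figures somewhat; it does not address the access rule.

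A reader might go further and conclude that the efficacy result is compromised. It is not: this point concerns exploratory analyses within one arm and leaves the QL+AR v QLO comparison as it stands. Nor does it show that AR is ineffective, only that these models cannot separate engagement from early abstinence.

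**What to change.** Change the analysis wording only; the unlock and suspension rules need not change.

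- Make the 48-hour (unlocked) set the main set for the Aim 2b and 3b predictor models, and do not interpret them in the full arm.
- Define engagement per opportunity: sessions per unlocked day, distinct locations per session, and on-demand coach contacts per unlocked week. Distinct locations level off as sessions accumulate, so counting them over the same fixed first sessions is the cleaner form.
- Measure extinction magnitude and latency over a pre-specified first number of sessions, with latency counted in sessions and not in calendar days, and state how participants with fewer sessions are handled.
- Show a sensitivity analysis adjusting for smoke-free days in weeks 1-5 or for 5-week smoking status, stating that it may remove a genuine AR effect.
- Report the results as associations, not as dose-response.

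The cost is SAP text; the daily diary and app metadata already supply the denominators. Fewer participants will contribute, associations will look weaker, and per-day rates can still be confounded by motivation.

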75% Accrual	Month 10	Month 34
100% Accrual	Month 10	Month 41

7. REGULATORY AND REPORTING REMINDERS

7.1 Institutional Review Board

No subject is to be enrolled on this protocol until the Center's Institution Review Board has approved it.

7.2 Informed Consent

The investigators and the researchers associated with the study are responsible for obtaining consent by the participants in a manner approved by the Institutional Review Board.

7.3 Investigator Study Files

Research records are the responsibility of the investigator.

They will be available for review by the sponsors of the trial, health care personnel involved in this study, the IRB, and the SRC.

The Principal Investigator will maintain study files for a period of years.

8. DATA SHARING

Data obtained from interviews, including both audio recordings and transcripts, will be shared with other investigators and institutions as approved to facilitate data analysis. These data could contain PHI.

Appendix of non-standard self-report surveys for AIM 1).

AIM 1 Augmented Reality Questions

1. Have you ever used any kind of augmented reality (AR) app before? (e.g., AR feature in Pokemon Go, IKEA or other furniture app, Snapchat filters, Google Sky Map, etc.)

- Yes
- No
- Don't know

2. How frequently do you use augmented reality (AR) apps?

- 7 days a week
- 4-6 days a week
- 1-3 days a week
- 1-5 times a month
- Less than once a month
- Never
- Don't know

3. How **interested** are you in using an augmented reality smartphone app?

IN App Daily Diary Questions:

URGE:

Cigarettes smoked prior day:

Please rate your urge to smoke on the scale below.

Daily Assessment

How many cigarettes did you smoke yesterday?

If you don't recall the exact amount just provide your best recollection.

Number (0-100)

Next

Did you use any of the following products yesterday? (check all that apply).

Nicotine Gum	
Nicotine Patch	
Nicotine Nasal Spray	
Prescription Nicotine Inhaler	
Nicotine Lozenge	
Zyban or Wellbutrin	
Chantix or Varenicline	
E-cigarette (e.g., vape pen, personal vaporizer, etc.)	
Other treatments or medications Specify: _____	

AIM 1: Feedback and app usage self-report measures

Reality/Coexistence items

Instructions: Please **mark** the number from 1-10 that represents how you feel about each question.

1. How real did the objects seem to you?

1	2	3	4	5	6	7	8	9	10
Not at All									Very Real

2. How well did the objects appear to be a part of the scene?

1	2	3	4	5	6	7	8	9	10
Not at All									Very Well

3. How much did you feel the objects were right there in front of you?

1	2	3	4	5	6	7	8	9	10
Not at All									Very Much

App Usefulness/Ease of learning/Satisfaction

1. Would this app appeal to you if you were currently attempting to quit smoking?

1	2	3	4	5
No, definitely not	No, I don't think so	Yes, I think so		Yes, definitely

2. At the beginning of the week, how easy or difficult was it to use the app?

1	2	3	4	5
Very Difficult				Very Easy

3. At the end of the week, how easy or difficult was it to use the app?

1	2	3	4	5
Very Difficult				Very Easy

4. How many days did it take to get comfortable using the app?

Choices are from 1 day - 7 days

5. Would you recommend this app to a friend or family member to help them quit smoking?

1	2	3	4
No, definitely not	No, I don't think so	Yes, I think so	Yes, definitely

6. Overall, how satisfied were you with the app?

1	2	3	4
Quite dissatisfied	Indifferent or mildly dissatisfied	Mostly satisfied	Very satisfied

ARC AIM 1 Follow-up Phone Interview (APP USE [AR ≥ 5])

"Hello, this is _____ from Project ARC. How are you today?"

"Thank you for setting time aside to give us feedback. I just have a few questions for you today."

General:

1. What did you think of the augmented reality smartphone app?
 - a. [probe for specifics if give general answers,] e.g., "It was good/weird/frustrating".

Rationale:

2. What do you think is the purpose of this app?
3. [TAM – perceived usefulness] Based on your recent experience quitting smoking, how do you think viewing smoking related images might be used while someone is trying to quit smoking?

Ease of use:

4. "What were the issues you encountered when navigating the app (e.g., ...)?"
5. [TAM – perceived ease of use] What was the easiest part of using the app?
6. [TAM – perceived ease of use] What was the most difficult part of using the app?
7. [TAM – attitude toward using] What was the most interesting part of using the app?
8. [TAM – behavioral intention to use] How would you tell your friends/family about this app if you were going to have them use the app to quit smoking?

New Features: I'm going to ask you about some specific features of the app.

9. In the app, there are three videos that explain how the AR sessions work, how they will help you stop smoking, and tips for the best AR experience. Did you watch these videos?
 - a. If yes, What did you find most helpful after watching these videos? What aspects of the videos can be improved?
 - b. If no, why did you not watch them? What recommendations may you have for improvement?
10. What are your thoughts on the instructions for doing the AR sessions?
 - a. What would have been helpful to know about doing AR sessions?
11. [TAM – perceived usefulness] After the three videos, there was a Practice Tutorial with a Rubber Ducky and the chance to practice an AR session. Did you practice?
 - a. If yes, what was helpful?
 - b. If no, why did you not practice?
 - c. What could we change to improve the practice experience? [Probe]
12. [TAM – perceived ease of use] When you started using the app, you had the chance to select 0, 1, or 2 reminder notifications. What did you select? Can you tell us why you choose this amount?
 - a. [TAM – perceived usefulness] If > 0, How did you feel about that number of reminders? Did they help remind you to complete AR sessions?
 - b. [TAM – perceived usefulness] If 0, Why did you opt out of reminder notifications?
 - c. What would you change about the reminder notifications?
13. In the app, there is a feature to track your progress (e.g., money and time saved, days abstinent, number of AR sessions completed).
 - a. I will list each progress feature, and I'd like you to tell me if you ever viewed it.
 - i. Days Remaining / Weekly Streak

- ii. # AR sessions Completed
- iii. Days Abstinent
- iv. Daily use of Nicotine Replacement Therapy
- v. Change in Urge
- vi. Money Saved
- vii. Time Saved
- b. [If Never used,] Why not?
- c. [For each progress feature ask;]
 - i. What about [feature] did you like?
 - ii. What about [feature] didn't you like? Why?
- d. [TAM – perceived usefulness] Did you find the progress feature useful as related to your quitting smoking?
- e. [TAM – perceived usefulness] Did you find the progress feature useful for your continued use of the app? (if question unclear, rephrase: In other words, did it make you more likely to continue using the app?)

14. After completing a certain amount of AR sessions, you had the ability to receive a reward. Did you ever receive a reward (as a reminder, the first one was a flower pot)? If no, skip a-d.

- a. [TAM – attitude toward use] What did you like about the rewards?
- b. [TAM – attitude towards use] What did you NOT like about them?
- c. [TAM – perceived usefulness] How did the rewards motivate you to do more AR sessions?
- d. [TAM – perceived usefulness or attitude towards use] What aspects of the AR rewards could be improved?

Improvements:

- 15. [TAM – behavioral intention to use OR attitude toward using] What type of changes would you make to the app to increase the likelihood of using it, or, to make it more enjoyable to use?
- 16. [TAM – behavioral intention to use] What other features could we include in the app to help someone continue using the app for quitting smoking?
- 17. What aspects would you change about the app?
- 18. What are the key points that you think we should talk to smokers about when explaining this app for smoking cessation?

Study team/Support:

- 19. [TAM – perceived ease of use] Did you ever reach out to the study team for help with the app?

If YES: What did you find helpful?

IF NO: Why not?

What other feedback do you have for us?

ARC AIM 1 Follow-up Phone Interview (NO/Little APP USE [AR < 5])

"Hello, this is _____ from Project ARC. How are you today?"

"Thank you for setting time aside to give us feedback. I just have a few questions for you today."

General:

1. We noticed that although you downloaded the app, you did not use the app/only used the app X times. It would help us to understand why you did not use the app (much). Can you tell me why you didn't use the app? Probe reasons.

2. What did you think about the description of the app during the study screening call and directions for use?
 - a. Were the descriptions and directions clear?
 - i. If not clear, what could have made it clearer?
 - b. What do you wish you were told before starting the ARC app?
 - c. When we first introduce this study to smokers in the future, what else should we tell them about the app to make sure they fully understand what they are being asked to do?

Rationale:

20. What do you think is the purpose of this app?

21. [TAM – perceived usefulness] How do you think viewing smoking related images might be used while someone is trying to quit smoking?

22. [TAM – behavioral intention to use] How would you tell your friends/family about this app if you were going to have them use the app to quit smoking?

Barriers:

23. [TAM – perceived ease of use] Can you tell me what made it difficult to use the app? (Probe all)
 - a. What would make it easier to use the app

24. [TAM – behavioral intention to use] What kind of strategies do you think would help motivate someone to continue using the app to help them quit smoking?

Study team/Support:

25. Did you ever reach out to the study team for help with the app?
 - a. If YES: Did you find it helpful? Why or why not?

26. Do you have any other feedback for the study team?
